**A Technology-Based Adaptive Intervention to Promote Cardiovascular Health after Completion of
Cardiac Rehabilitation (Mobile4Heart)**

[name], MS, FNP-BC, FAAN, FAHA

NCT03446313

Protocol Date: 02/23/2018

Background

While numerous studies have examined barriers to cardiac rehabilitation (CR) and patient outcomes immediately following CR, few have investigated long-term adherence to secondary prevention behaviors and outcomes of patients who complete CR. Ongoing maintenance of physical activity after CR is an important part of preventing secondary cardiac events in patients with ischemic heart disease. However, it is well-documented that after discharge from a CR program, many patients return to a sedentary lifestyle. Applying mobile health strategies as a method of increasing adherence by providing education and support holds much promise.

Close monitoring after CR completion has been shown to be an effective strategy for improving patient adherence to program recommendations. In addition, interventions involving continued communication between patient and health care provider post-immediate discharge decreases hospital readmissions. Post-CR monitoring through mobile technology may be an effective strategy for improving patient adherence.

Our central hypothesis is that monitoring and promotion of health-related behaviors by increasing patient-provider communication through a mobile device after discharge from a CR program increases adherence to a 'heart healthy' prescription over an extended period of time. Through a mixed-methods study design, we will examine the efficacy of mobile technology to promote secondary prevention behaviors including physical activity as an extension of an outpatient CR program. The intervention includes use of a mobile phone app (MVN) for physical activity and healthy lifestyle behaviors such as medication adherence, nutrition, stress management, smoking cessation, etc. We will apply an adaptive design that accounts for varying levels of adherence from baseline to 2 months (N=60).

The specific aims of this randomized clinical trial comparing the intervention group (MVN app and Fitbit) to the control group (pedometer only) will:

1. Evaluate differences in physical activity.
H₀: The MVN group will have more physical activity (measured by an activity tracker) and better 6 minute walk tests compared to Usual Care.
2. Determine differences in depression and self-efficacy to continue exercise.

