H₀: The MVN group will have less depression and higher self-efficacy compared to Usual Care.
3. Assess usability and satisfaction with using a smartphone application for participation in a post-CR cardiac health program.
H₀: The MVN group will report high usability and satisfaction with the MVN app.

Study Design

Mixed methods study with a randomized controlled trial and usability study with individual interviews.

Selection of Subjects / Setting

We plan to enroll up to 60 participants from John Muir Medical Center (JMMC). JMMC is a non-profit, community hospital system consisting of two large medical campuses and 3 CR locations (Brentwood, Concord, Walnut Creek). Participants will be randomized through a computer program to either the intervention group (Mvn app) or control group (usual care).

Inclusion criteria:

1. ≥ 18 years of age
2. History of cardiovascular disease that qualified patient for cardiac rehabilitation (i.e., ischemic heart disease, history of unstable angina, systolic heart failure with ejection fraction =/ $< 35\%$ and Class II to IV symptoms, coronary artery bypass graft surgery, valve replacement)
3. Within eight weeks of completing outpatient cardiac rehabilitation

Exclusion criteria:

1. Cognitive impairment
2. Lack of English proficiency/literacy
3. Clinically conditions including:
 - a. Unstable arrhythmias, aortic stenosis, thrombophlebitis, dissecting aneurysm or symptomatic anemia
 - b. Active infection
 - c. Uncontrolled hypertension: resting diastolic > 100 mmHg, systolic > 180 mmHg
 - d. Decompensated heart failure NYHA Class 3-4
 - e. Current unstable angina (No chest pain for a month)
 - f. 2nd or 3rd degree heart block
 - g. Uncontrolled high grade exercise-induced ventricular ectopy-hemodynamically stable

Both Usual Care and MVN Intervention groups

- Upon completion of the CR program, participants will be given their standard instructions and educational handouts
- Individuals will meet with their nurse or other health care provider in an exit interview to review their exercise progress, discuss their future exercise goals and plans, and receive referrals to additional medical services they might need after discharge from the program.
- Baseline clinical measurements, including a 6 minute walk

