- An activity tracker will be given to each participant. Participants randomized to the intervention group will receive a Fitbit and instructions on how to sync their data. Participants randomized to the control group will receive a basic pedometer with a paper diary to record their step counts each day.
- Questionnaires will ask about health care utilization, physical activity, quality of life, and self-efficacy.
- The clinical measurements and psychosocial questionnaires will be taken again at 2-months.
- Participants will be paid \$50 in the form of a gift card for each month they complete. Participants that participate in the individual interview will receive an extra \$25 card. Participants in the intervention group will be allowed to choose whether they would like to keep the Fitbit or receive the gift cards. Participants in the control group will be allowed to keep their pedometer and will also receive the gift cards. If a participant withdraws from the study before month two, they will be asked to return their devices.

MVN Group Only:

- During the final week of outpatient cardiac rehabilitation, the MVN application will be downloaded on to the participant's smartphone or tablet. If the participant does not have a smartphone or tablet, a smartphone will be provided to them for the duration of the study. The participant will be required to return the smartphone at the end of their participation in the study.

- Each participant's individualized instructions for post-cardiac rehabilitation will be integrated into the MVN application including daily medication reminders, physical activity prompts, educational materials, and patient-reported outcome assessment of behavior and psychosocial status.
- Text messages or phone calls will be used on an ad hoc basis to provide positive feedback to the participant. Frequency of messages will depend on adherence level (adaptive intervention).
- We will apply an adaptive intervention: a sequence of decision rules that specify how the intensity or type of treatment should change depending on the patient's needs. We are developing sequential, multiple assignment, randomized trials (SMART) to enable scientists to build adaptive interventions. Interventions that adapt at the right times can improve participant outcomes (e.g., intensifying for people who do not respond to the initial treatment) while decreasing the cost and burden of the intervention (e.g., stepping down treatment for responsive participants).

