- Regular messages will be based on the American Heart Association Simple 7 Principles (3 times a week on random days and between 9am-6pm). Examples include prompting participants to engage in physical activity, track their medicine at certain times of the day, engage in healthy eating habits, or provide participants with a homework assignment to reinforce educational content regarding risk management.
- Any patient reports of chest pain or acute shortness of breath will immediately prompt an automated message on the app to call 911 or their cardiologist/primary care provider. The consent will specify the research members including nurse will only monitor app use but not play an integral role in provided one-on-one coaching.
- A registered nurse or nurse practitioner will be available to triage patient entries once a day (mid-afternoon). Two-way messaging between the participant and the nurse will be available to provide opportunities to answer more specific questions.
- Technical support will be provided by Moving Analytics who has developed and own the MVN app.
- We will assign patients to a group of 6 individuals to offer social support and a "buddy system", which will be a feature in the secure MVN app. Ideas for these groups may be sharing exercise tips/goals/progress, recipes, etc. The groups will be formed with consecutive enrollment. The function of the social group will be iterative with regular feedback from the group members that will be sent to the research assistant to improve this feature.
- Up to six participants from the intervention group will be asked to complete an individual interview to assess the feasibility of and their satisfaction with the mobile app over the two month period.

Study Activities:

Activity	Usual Care	MVN	Intervals
MVN mobile app		X	Intervention period
Educational materials	X	X	Baseline
Activity tracker	X	X	Intervention period
Step count diary	X		Intervention period
Physical activity prompts		X	Intervention period
Nurse feedback (through app or by phone)		X	Intervention period
Psychosocial questionnaires	X	X	Baseline, Month 2

Blood pressure/heart rate	X	X	Baseline, Month 2
Weight	X	X	Baseline, Month 2
6 minute walk	X	X	Baseline, Month 2

Intervention period: 2 months

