**[name], MS, FNP-BC, FAAN, FAHA**

**NCT03446313**

**Statistical Analysis**

**04/23/2019**

P-values for baseline tests were calculated from two-sample t-tests (or Wilcox rank-sum test if skewed) or chi-squared tests.

We analyzed the primary outcome of step count difference between the two groups over 60 days fitting linear mixed-effects models with the step count for each day in R (version 3.6.0). For a more precise estimate of the treatment effect, we used a step-wise procedure to include potential covariates impacting the outcome (age, gender, working status, college or higher education, relationship status, depression, self-efficacy, and self-reported PA), including only terms that were significant in the model. The 2-sided significance level was established a priori at an alpha of 0.05. We employed an intention-to-treat analysis approach. We tested our secondary outcome of the standardized change score in 6MWT from baseline and 2 months also using linear mixed models, with the same approach. The covariate association of depression and self-efficacy for step count difference and 6MWT were also considered to be secondary questions of interest.

Since our analysis included a small amount of missing data for the covariates (education missing on 8%, all other covariates <4%), our analyses used multiple imputation by chained equations, using 5 imputations. Results differed very little compared to complete case analysis.

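### Protocol Aim 2 predicts between-arm differences in depression and self-efficacy, but the SAP text available gives neither score a between-arm follow-up analysis

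*SAP*

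**What the plan says.** The protocol's second specific aim is to "Determine differences in depression and self-efficacy to continue exercise". Its hypothesis gives a comparator and a direction: "The MVN group will have less depression and higher self-efficacy compared to Usual Care". The aims are introduced as those of a randomized trial of the app-plus-Fitbit arm against the pedometer arm.

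On data collection, the protocol's section on procedures common to both groups says: "Questionnaires will ask about health care utilization, physical activity, quality of life, and self-efficacy", and then "The clinical measurements and psychosocial questionnaires will be taken again at 2-months". The Study Activities table has a row for "Psychosocial questionnaires", marked for both arms at baseline and Month 2. Self-efficacy is among the listed questionnaire topics. Depression is not, and no depression instrument is named.

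The SAP (Statistical Analysis, dated 04/23/2019) makes daily step count over 60 days the primary outcome. It names one secondary outcome, in the singular: "We tested our secondary outcome of the standardized change score in 6MWT from baseline and 2 months also using linear mixed models". Depression and self-efficacy are candidates in the step-wise covariate selection, and they appear once more: "The covariate association of depression and self-efficacy for step count difference and 6MWT were also considered to be secondary questions of interest". The two-sample and chi-squared tests are described as baseline tests.

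**The concern.** Aim 2 asks whether assignment to the app changes depression and self-efficacy. In the SAP these scores are explanatory variables for steps and walking distance. An association between, say, self-efficacy and step count is not protected by randomization. It could be strong if the app had no effect on self-efficacy, or absent if the app had a large one.

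An analyst who followed the available SAP text would finish without an estimate, interval or test for a numbered aim. Because the SAP calls the covariate association a secondary question, a reader could also take it for the Aim 2 result.

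**Working it through.** **Outcomes against analyses.** The SAP states no figure on this point, so the check is a comparison of the two documents.

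| Outcome in Aims 1 and 2 | Between-arm follow-up analysis in the available SAP text |
|---|---|
| Physical activity (steps) | Yes: mixed model, primary |
| 6-minute walk | Yes: mixed model on standardized change, secondary |
| Depression | None: candidate covariate and association only |
| Self-efficacy | None: candidate covariate and association only |

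Both Aim 1 outcomes are covered and neither Aim 2 outcome is.

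**Could other SAP wording cover Aim 2?**
- The remark that the same approach was used belongs to the sentence on the walk test. It comes before the psychosocial scores are mentioned as secondary questions.
- The baseline tests may compare the arms on these scores, but a baseline comparison says nothing about a treatment effect.
- The association sentence has steps and 6MWT as the outcomes and the scores as covariates.

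**Were Month-2 scores planned?** For self-efficacy, yes: it is a listed topic and the questionnaires are repeated at two months. For depression, the documents are indirect. The SAP uses it as a covariate and reports less than 4% missing for every covariate except education (8%), so it was measured at least once. The SAP does not say at which visit.

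**What precision could the missing comparison have?** The documents give "We plan to enroll up to 60 participants" and a two-sided alpha of 0.05. The rest is assumed: 30 per arm (full enrolment, 1:1 allocation) or 24 per arm (20% missing, 30 × 0.8); baseline to Month-2 correlation ρ of 0.3, 0.5 or 0.7; and alpha 0.025 if the two tests are corrected for multiplicity (0.05 / 2).

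For a comparison adjusted for the baseline score, in SD units:

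- SE = √[(2/n)(1 − ρ²)]
- Difference detectable with 80% power = (z₁₋α/₂ + 0.8416) × SE
- 95% CI half-width = 1.96 × SE

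Example, n = 30, ρ = 0.5, alpha 0.05: SE = √(0.0667 × 0.75) = 0.2236, so the detectable difference is 2.8016 × 0.2236 = 0.626 and the half-width is 1.96 × 0.2236 = 0.438.

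| Case | ρ = 0.3 | ρ = 0.5 | ρ = 0.7 |
|---|---|---|---|
| Detectable, n = 30, alpha 0.05 | 0.690 | 0.626 | 0.517 |
| Detectable, n = 30, alpha 0.025 | 0.759 | 0.689 | 0.568 |
| Detectable, n = 24, alpha 0.05 | 0.771 | 0.700 | 0.578 |
| Detectable, n = 24, alpha 0.025 | 0.849 | 0.771 | 0.636 |
| 95% half-width, n = 30 | 0.483 | 0.438 | 0.361 |
| 95% half-width, n = 24 | 0.540 | 0.490 | 0.404 |

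With the noncentral t distribution (2n − 3 degrees of freedom) the first row becomes 0.702 / 0.637 / 0.525 and the fourth 0.874 / 0.793 / 0.654. These slightly larger values are the better guide at this sample size.

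**The case against.** The omission itself is hard to dispute. The case on the other side concerns its size and the remedy.

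- **Depression was probably in the repeated battery.** Aim 2 names it, the SAP has a depression covariate, and the psychosocial questionnaires are scheduled again at two months. This is the natural reading, but no sentence confirms it, so a request to state which instruments were given when is enough.
- **The power figures do not show the omission.** This is correct. They describe only what the added analysis could deliver, and all inputs except the planned N and alpha 0.05 are assumed. The half-widths are also for 95% intervals. If alpha 0.025 were used, the matching 97.5% half-width at 24 per arm and ρ = 0.3 would be 2.2414 × 0.2754 = 0.62 SD.
- **Nothing in the documents requires ANCOVA.** A mixed model or a change-score comparison would also answer the aim. ANCOVA is suggested because it is simple and no less precise in large samples: with equal variances at the two visits, the variance factor at ρ = 0.5 is 1 − 0.25 = 0.75, against 2(1 − 0.5) = 1.00 for a change score. Multiplicity and imputation are secondary details.
- **The SAP never presents the association as the Aim 2 result.** This is true, and no intent to substitute is alleged. The aim is nonetheless left unanswered, and the association is the only analysis that bears on these two scores after baseline.
- **Part of the SAP file was not available for review.** If the analysis is specified there, a cross-reference settles the point.

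**Conclusion.** The concern holds for the SAP text available. A directional, randomized hypothesis in a numbered aim has no between-arm analysis for either of its two outcomes, and the one analysis that involves those scores answers a different question. This should be fixed, but it does not bias the step-count or 6-minute walk treatment effects.

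For self-efficacy the gap is an analysis omission. For depression it is the same if the score was collected at Month 2. If it was not, the gap lies in data collection and SAP wording cannot repair it.

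Under the stated assumptions the added comparison could detect only fairly large differences, about 0.53 to 0.87 SD (noncentral t), with 95% half-widths of about 0.36 to 0.54 SD. That is a reason to report an estimate with its interval and not rely on a p-value. It is not a reason to leave the aim out.

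**What to change.** In the SAP:

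1. Name the depression and self-efficacy instruments and the visits at which each was given, and state whether depression was collected at Month 2.
2. Add Month-2 self-efficacy, and Month-2 depression if collected, as secondary outcomes. Compare the arms as randomized by ANCOVA with the baseline score as covariate, and report the adjusted difference with its 95% CI. State whether the two tests are corrected for multiplicity.
3. Report missing Month-2 scores by arm. If they are imputed, use a separate imputation model containing arm and both visits' scores, so that the step-count and walk-test results do not change.
4. Label these comparisons as specified after the SAP's analyses were run (the SAP is written in the past tense), while noting that the hypothesis is in the protocol.
5. Label the covariate association exploratory and state that it does not answer Aim 2.
6. If depression was not collected at Month 2, or Aim 2 was dropped or changed, say so and give the reason.

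The cost is a few sentences, one or two regressions, one table of missing scores and a check of the Month-2 questionnaires. It needs no new patients and, with imputation kept separate, no re-run of existing analyses. The drawbacks are limited precision and the post hoc status of the model.

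### Depression and self-efficacy associations are declared secondary questions, but the only models the SAP describes drop a covariate that is not significant

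*SAP*

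**What the plan says.** All the relevant text is in the SAP, under Statistical Analysis.

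- **Candidates.** The pool has eight covariates: "age, gender, working status, college or higher education, relationship status, depression, self-efficacy, and self-reported PA".
- **Purpose of the selection.** "For a more precise estimate of the treatment effect, we used a step-wise procedure to include potential covariates impacting the outcome". No other purpose is given.
- **Retention rule.** The model is built "including only terms that were significant in the model". No covariate is said to be forced in, and no separate entry or removal threshold is given. The only level stated is the general one: "The 2-sided significance level was established a priori at an alpha of 0.05".
- **6MWT.** "We tested our secondary outcome of the standardized change score in 6MWT from baseline and 2 months also using linear mixed models, with the same" method as for step count.
- **Status of the associations.** "The covariate association of depression and self-efficacy for step count difference and 6MWT were also considered to be secondary questions of interest".

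The SAP describes no other model for these associations and does not say how a covariate that is not retained would be reported. The protocol fills neither gap. Its second aim, "Determine differences in depression and self-efficacy to continue exercise", concerns between-group differences in these two measures, not their association with steps or 6MWT.

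**The concern.** A step-wise filter aimed at precision of the treatment effect treats covariates as nuisance terms, and it does not matter to that aim which of them survive. Once the coefficient of a covariate is itself a declared question, the same filter decides both whether the question gets an answer and whether the answer is significant.

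If the four associations are taken from the selected models, two things follow. A term that is dropped leaves no estimate and no interval, so a weak or null association cannot be shown as such. A term that is kept has passed a significance test already, so the p-value printed beside it is not a fresh test and the estimate tends to be too far from zero. Which of the four associations get reported would then depend partly on chance.

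**Working it through.** The documents give no effect size, SD or power calculation for these associations, so there is no stated figure to reproduce. What can be checked is how the retention rule behaves.

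**Inputs from the documents.** Eight candidates, significant terms only, two-sided 0.05 (SAP); "We plan to enroll up to 60 participants from John Muir Medical Center (JMMC" (Protocol, Selection of Subjects / Setting).

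**Assumptions.** N = 60; retention at p < 0.05; backward elimination with group always kept; one outcome value per participant; standardised covariates; residual SD 1; treatment effect 0.3 SD in the independent-covariate runs. Slopes are in outcome SD per covariate SD and are given as magnitudes.

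**Step 1: approximate arithmetic, independent covariates.**
- Standard error of a slope ≈ 1/√60 = 0.129.
- Smallest estimate that can be kept ≈ 2.00 × 0.129 = 0.258. A true slope of 0.2 can therefore be kept only when it is overestimated.
- For a true slope of 0.2: z = (0.258 − 0.2)/0.129 = 0.45. The chance of being kept is 1 − Φ(0.45) = 0.326. The mean when kept is 0.2 + 0.129 × φ(0.45)/0.326 = 0.2 + 0.129 × 0.3605/0.326 = 0.343, or 1.7 times the truth.
- For a true slope of 0.5: z = (0.258 − 0.5)/0.129 = −1.88. The chance of being kept is about 0.97. The mean when kept is 0.5 + 0.129 × 0.0687/0.97 = 0.509, an inflation of about 2%.

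**Step 2: simulation, independent covariates (4,000 trials per row).**

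| True slope | Kept | Mean kept ÷ truth | 95% CI coverage when kept |
|---|---|---|---|
| 0 | 4.8% | – | 0% |
| 0.1 | 12% | 2.93 | 75% |
| 0.2 | 33% | 1.72 | 92% |
| 0.3 | 60% | 1.27 | 95% |
| 0.4 | 83% | 1.10 | 97% |
| 0.5 | 95% | 1.03 | 96% |
| 0.7 | 99.8% | 1.00 | 94% |

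The rows for 0.2 and 0.5 agree with step 1. With N = 50 the ratio at a slope of 0.2 rises to 1.86. With all eight covariates kept regardless of significance (N = 60), the mean estimate at a true slope of 0.2 is 0.203, and coverage is 94.6–95.6% across the slopes.

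**Step 3: simulation, correlated covariates, true depression slope 0.2.**

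| Other covariates | Kept | Mean kept | Ratio to 0.2 | Coverage when kept |
|---|---|---|---|---|
| Independent, no effect | 33% | 0.345 | 1.72 | 92% |
| Depression correlated −0.4 with self-efficacy and self-reported PA, which have no effect | 29–31% | about 0.35 | about 1.75 | 87–91% |
| Same correlations, self-efficacy and PA each with a 0.2 effect | 42–43% | 0.42 | 2.1 | 67% |

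The last row mixes two sources of bias: selection for significance, and confounding when a correlated predictive covariate is dropped.

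**Step 4: does a smaller fixed model also work?** A model with group, depression and self-efficacy only, in the setting of the last row and with self-efficacy and PA taken as uncorrelated, estimates −0.20 + 0.2 × (−0.4)/(1 − 0.4²) = −0.20 − 0.095 = −0.295. Simulation gave −0.29 to −0.30, with 90% coverage of the PA-adjusted value of −0.20, against 95% for the model with all eight covariates. The smaller model is not affected by selection, but it estimates a different, less-adjusted association.

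**The case against.** **The SAP does not say that the step-wise models answer these questions.** This stands. It ties the step-wise rule to the treatment effect and names the associations in a separate sentence, so a separate model, or keeping the two terms throughout, is not excluded. Nor does it say that a dropped term goes unreported. What can be said is that no other model is described and that the one described is unsuitable for this purpose. If another model was used, the SAP needs to state it.

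**The bias may be small.** This also stands in part. A reader might infer that every answer must be either missing or materially inflated. The figures do not support that: with independent covariates the inflation is 10% at 0.4 SD and 3% or less from 0.5 SD, and the documents do not give the true slopes. The lowest coverage arises only when self-efficacy and self-reported PA are themselves predictive and correlated with depression.

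**The threshold is assumed.** Correct. The SAP gives no retention level apart from the general 0.05. A different level would change the sizes but not the mechanism.

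**Sixty days of step counts per person supply ample data.** This does not help if, as is natural, depression and self-efficacy enter as one value per participant. Their slopes are then informed by about 60 people however many days each contributes. The 6MWT change score has one value per participant in any case.

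**These are only observational side questions.** They are observational, but the SAP calls them secondary questions, so they need a method that can answer them.

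**Conclusion.** The point holds as a gap in specification with a predictable consequence. Four associations are declared secondary questions, and the only models described would yield either no estimate or one selected for significance. If those models are used, kept estimates are biased away from zero in expectation and their p-values are not valid tests.

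Under the assumptions listed, a true slope of 0.2 SD would be kept in about 30–43% of trials and overstated by a factor of about 1.7 to 2.1 when kept, with coverage running from 92% down to 67%. A true null that is kept always has an interval that excludes zero. The near-absence of inflation from about 0.5 SD was computed with independent covariates and need not carry over to correlated, predictive ones.

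Confidence is high in the conflict within the SAP text and in the direction of the bias, but lower in its size. A reader might also infer that the estimated treatment effect is compromised. Nothing here shows that; the point concerns these four associations only. It should be corrected, but it does not threaten the primary analysis.

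**What to change.** Take the four associations out of the step-wise procedure. Fit one model per outcome (step count, 6MWT) with a fixed covariate set that always includes group, baseline depression and baseline self-efficacy.

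State the adjustment set and the reason for it:
- all eight listed covariates, if the fully adjusted association is the target;
- group, depression and self-efficacy only, if the less-adjusted association is the target.

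Either choice removes the selection problem, but they answer different questions. The 95% coverage quoted for the fully adjusted slope belongs to the first. The SAP is written in the past tense, so the models may already have been fitted. If so, the set should be chosen from the question and not from the results, and the added models should be identified as such.

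Report all four coefficients with 95% confidence intervals whatever their significance, labelled as observational associations. A fixed set also avoids having to explain how selection was combined across the five imputations, which the SAP leaves unstated.

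The cost is a change of SAP wording and two extra regressions on data already held. The downside is that some reported associations will be smaller or not significant.

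### The depression and self-efficacy associations have no model of their own: they come from a step-wise precision model that may condition on self-reported activity or drop the term altogether

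*SAP*

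**What the plan says.** The SAP's Statistical Analysis text takes daily step count over 60 days as primary: "We analyzed the primary outcome of step count difference between the two groups over 60 days fitting linear mixed-effects models". Covariates enter for one stated purpose: "For a more precise estimate of the treatment effect, we used a step-wise procedure to include potential covariates impacting the outcome". The candidate list ends with "depression, self-efficacy, and self-reported PA), including only terms that were significant in the model". The 6MWT change score is handled in the same way.

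The SAP then raises a second use of the covariates: "The covariate association of depression and self-efficacy for step count difference and 6MWT were also considered to be secondary questions of interest". No separate model, forced-in term or covariate time point is given for that use.

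The Protocol's first aim defines the activity outcome by device: "The MVN group will have more physical activity (measured by an activity tracker". Its section on procedures common to both groups lists physical activity and self-efficacy among the questionnaire topics. The Study Activities table schedules the psychosocial questionnaires at baseline and Month 2.

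**The concern.** A covariate set chosen to reduce residual variance in a randomized comparison need not suit a question about how one covariate relates to the outcome. Two problems follow.

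- **Conditioning.** Self-reported PA is a questionnaire measure of the construct that the tracker measures. With it in the model, the self-efficacy coefficient says whether self-efficacy relates to steps among people who report equal activity. That is a narrower question than whether self-efficacy relates to steps, and its coefficient will usually be smaller. Forcing every term in would not cure this.
- **Selection.** Only significant terms stay. A depression or self-efficacy term that misses 0.05 is removed, so a declared secondary question gets no estimate or interval. A term that stays has been selected partly for being large.

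A reader could take a missing or small coefficient as evidence that mood and self-efficacy do not matter for activity after rehabilitation, when the model was never set up to answer that.

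**Working it through.** The plan states no effect size, correlation or power for these associations, so there is no figure to reproduce. Taken from the documents: up to 60 participants (Protocol, Selection of Subjects / Setting), two-sided alpha 0.05, and the candidate list and retention rule (SAP). **All correlations below are assumptions.**

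**1. One psychosocial measure x, outcome y (mean steps), self-reported PA z.**

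Standardized coefficient: b = (r_xy − r_xz·r_zy) / (1 − r_xz²).
Partial correlation: (r_xy − r_xz·r_zy) / √[(1 − r_xz²)(1 − r_zy²)].
Power by Fisher's z, N = 60, with r_xy = 0.30:

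| r_xz | r_zy | b | Loss | Partial r | Power |
|---|---|---|---|---|---|
| z not in model | – | 0.30 | – | 0.30 (unadjusted) | 0.65 |
| 0.3 | 0.4 | (0.30 − 0.12)/0.91 = 0.198 | 34% | 0.206 | 0.35 |
| 0.4 | 0.5 | (0.30 − 0.20)/0.84 = 0.119 | 60% | 0.126 | 0.16 |
| 0.5 | 0.5 | (0.30 − 0.25)/0.75 = 0.067 | 78% | 0.067 | 0.08 |

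**2. When does the coefficient shrink?** For positive r_xy and r_xz, b is below r_xy when r_zy > r_xy·r_xz. With r_xy = 0.30 and r_xz from 0.2 to 0.5, the threshold is 0.30 × 0.2 = 0.06 to 0.30 × 0.5 = 0.15. Even a weak link between reported and measured activity is enough.

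**3. The direction is not guaranteed.** Take depression–steps at −0.30:

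- PA–steps 0.3, depression–PA −0.2: −0.25
- PA–steps 0.5, depression–PA −0.5: −0.067
- PA–steps 0.7, depression–PA −0.5: +0.067 (sign reversed)
- PA–steps 0, depression–PA −0.5: −0.400 (larger)

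**4. Both psychosocial measures together.** Assume depression–steps −0.30, self-efficacy–steps +0.30, depression–self-efficacy −0.40 and self-efficacy–PA +0.30. Without PA, mutual adjustment alone gives (−0.30 + 0.12)/0.84 = −0.214 for depression and +0.214 for self-efficacy. Adding PA:

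| PA–steps | Depression–PA | Depression | Self-efficacy |
|---|---|---|---|
| 0.40 | −0.20 | −0.183 | +0.129 |
| 0.60 | −0.20 | −0.162 | +0.071 |
| 0.40 | 0 | −0.268 | +0.080 |
| 0.00 | −0.20 | −0.226 | +0.245 |

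The first two rows shrink both coefficients. The third enlarges depression and shrinks self-efficacy. The last enlarges both.

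**5. The retention rule.** This was simulated by backward elimination at 0.05 with N = 60, arm forced in, five noise covariates and the step 4 correlations (depression–PA −0.20). One outcome per participant is used, a simplification of the mixed model.

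| PA–steps | PA kept | Depression kept | Self-efficacy kept | Mean depression if kept | Mean self-efficacy if kept |
|---|---|---|---|---|---|
| 0.10 | 7% | 46% | 43% | −0.371 | +0.373 |
| 0.40 | 77% | 39% | 27% | −0.337 | +0.336 |
| 0.60 | 99.8% | 37% | 16% | −0.284 | +0.262 |

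In every row each true association goes unreported more often than not. When one is reported, selection has inflated it: at PA–steps 0.40 the unselected adjusted values are only −0.183 and +0.129.

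**The case against.** The strongest reply is that self-reported PA is only a candidate and that nothing in the documents shows it was kept. Its timing is also not stated. A baseline value precedes the 60-day outcome period and could be a common cause of exercise self-efficacy and later steps, so adjusting for it would be ordinary confounding control. A Month 2 value would make the objection much stronger. This stands: it rules out claiming a certain bias, and it shows that the SAP must state the timing.

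A reader might infer that self-reported PA is the outcome measured a second time, so that activity is held fixed. The documents do not support that. It is a different instrument, and the assumed correlation of 0.4 to 0.5 with steps means only 16% to 25% shared variance.

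A reader might also extend the argument to 6MWT. A change in walk distance is not a measure of physical activity, so the same-construct argument fails there. The selection problem and the lack of a dedicated model still apply.

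Nor does the Protocol's second aim, "Determine differences in depression and self-efficacy to continue exercise", settle what is intended. It concerns differences between arms in these measures as outcomes, not their association with steps.

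Finally, the SAP's term covariate association fits reading adjusted coefficients, and preferring an association free of PA is partly a choice of question. That is fair, and it argues for showing both versions. It does not defend leaving the choice to significance testing.

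**Conclusion.** The point holds in limited form. The SAP names four secondary associations and leaves what each one estimates to a selection procedure designed for something else. Two consequences follow from the text: each coefficient is conditional on whatever else survived, and a non-significant psychosocial term receives no estimate.

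Attenuation of the step-count associations is likely if self-reported PA is retained and correlations run the expected way. It might be tempting to say that both associations are necessarily pushed toward zero. The documents do not support that: growth and sign reversal are arithmetically possible, and significance-only retention enlarges the coefficients that survive. The 34% to 78% loss and the fall in power rest wholly on assumed correlations with PA of 0.3 or more and are illustrations only. The randomized comparison of arms is not affected, so this is a worthwhile correction to secondary questions and does not threaten the main result.

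**What to change.** Keep the precision covariates for the treatment-effect model only. Estimate each of the four associations (depression and self-efficacy, each with step count and with 6MWT change) in its own specified model, with arm, age, gender and the baseline value of the psychosocial measure forced in regardless of significance. Report each coefficient with its interval twice: without, and then with, baseline self-reported PA and the other psychosocial measure. Label the second as conditional on reported activity, and state the time point of every covariate.

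The cost is a few sentences in the SAP, a few short models on data already held, and two coefficients per association to interpret. The version without PA leaves prior activity unadjusted, which the second coefficient covers. The SAP is written in the past tense; if the analysis has already been run, the added models should be labelled as added afterwards.
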